2.2.1 Clinical Data to Date

Tranexamic acid is a synthetic derivative of the amino acid lysine. Its mechanism of action is via inhibition of fibrinolysis by blocking the lysine binding site on plasminogen. It acts as a competitive inhibitor of conversion of plasminogen to plasmin and at higher concentrations a non-competitive inhibitor of plasmin.

Thrombin is a serine protease coagulant that both converts soluble fibrinogen into insoluble fibrin strands and activates factor XIII to catalyze covalent crosslinking of these strands, thereby forming a stable fibrin clot. It also promotes platelet aggregation at the site of vascular injury, via the activation of specific protease-activated receptors. Thus, exogenous topical thrombin directly activates the terminal stages of blood clot formation at the site of application.

Bupivacaine is an amino-amide local anesthetic. Onset of action is 1-17 min. Duration of action (route and dose-dependent) 2-9 hr. Half life: neonates 8.1 hours, adults: 2.7 hours. Time to peak plasma concentration (for peripheral, epidural, or caudal block): 30-45 min. Protein binding: about 95%. Metabolism: hepatic. Excretion: renal (6% unchanged).

Lidocaine is an amino-amide local anesthetic. Onset of action is 2-4 min. Duration of action (route and dose-dependent) 2 - 3.5 hr. Half life: 1.5-2 hr. Protein binding: 60-80%. Metabolism: hepatic. Excretion: renal.

Previous work by our group showed that the addition of topical thrombin to local anesthetic at the end of elective hand surgery provides for sustained postoperative pain control. Patients in that study who received thrombin and local anesthetic before wound closure had lower pain levels and were discharged from the PACU sooner than those who received local anesthetic alone. We hypothesize that the addition of a topical antifibrinolytic agent such as tranexamic acid with thrombin and local anesthetic at the end of elective hand surgery will provide even greater pain relief through the formation of a stable clot that prolongs the effect of local anesthesia. We hypothesize we will see even lower pain scores and lower number of pain pills and shorter PACU times in the postoperative period in the groups with a tranexamic acid + thrombin + local anesthetic than the groups with just thrombin + local anesthetic.

2.2.2 Dose Rationale (if applicable)

The dosages that we use for treatment groups 1 and 2 in this research study are consistent with the dosages given per standard of care at this institution. Treatment groups 1 and 2 are considered equivalent and are both used in our practice as standard of care.

Previous literature has shown that topical application of tranexamic acid and aminocaproic acid decreases postsurgical bleeding after major surgical procedures, and that this is a promising strategy to improve surgical outcomes (Ipema H et al., Use of topical tranexamic acid or aminocaproic acid to prevent bleeding after major surgical procedures). Clinical trials, case reports, and meta-analyses describing topical use of tranexamic acid or aminocaproic acid to prevent postoperative bleeding all

CONFIDENTIAL

This material is the property of the NYU School of Medicine and Langone Medical Center. Do not disclose or use except as authorized in writing by the study sponsor
Interventional Template Version: 11 January 2019

showed reduction of postoperative blood loss. The dosages used in these studies are as follows: 4 trials used solutions containing tranexamic acid (1-2.5 g in 100-250 mL of 0.9% NaCl), and 1 trial assessed a solution containing aminocaproic acid (24 g in 250 mL of 0.9% NaCl).

Literature has shown that topical TXA is safe and effective for reducing perioperative blood loss. It is therefore a great agent for controlling perioperative blood loss and potentially lowers transfusion rates and shortens length of hospital stay (Wei W et al., Comparison of intravenous and topical tranexamic acid in total knee arthroplasty). Off-label use of topical TXA in surgery has demonstrated that patients who received topical TXA were associated with a shorter length of hospital stay (Teoh T et al., Prophylactic Topical Tranexamic Acid Versus Placebo in Surgical Patients A Systematic Review and Meta-Analysis*).

Tranexemic acid: We plan on using a total dose of 500 mg (20 mL) total for each case.

Aminocaproic acid: We will use a total of 1000 mg total for each case.

Recombinant Human Thrombin: For our topical application, we will use a total of 10000 units per open surgical study arm involving use of Thrombin.

Lidocaine Hydrochloride with Epinephrine: We plan on using a total of 5 mLs per open surgical study arm involving lidocaine hydrochloride and epinephrine.

Bupivacaine Hydrochloride with Epinephrine: We plan on using a total of 5 mLs per open surgical study arm involving bupivacaine hydrochloride with epinephrine.

Each study arm will receive an intraoperative local block at the site of surgery by the operative surgeon prior to incision, in accordance with our institutional standard of care..

2.3 **Rationale**

Pain management immediately post operatively is often difficult without utilizing opioids. With increasing concern about opioid addiction, our study hopes to elucidate other methods of immediate post operative pain control that will limit the amount of opioids taken after having elective hand surgery.

We propose that the utilization of thrombin, topical anesthetic, and an antifibrinolytic will improve post operative pain control.

2.4 **Potential Risks & Benefits**

2.4.1 **Known Potential Risks**

Lidocaine: Tinnitus, cardiac irritability, and neurological disturbance have been noted only when patients receive more than 4mg/kg of lidocaine. In this study, we are using less than 1mg/kg, which is a lot lower than the maximum amount of medication given to patients.

Bupivacaine: Tinnitus, headache, difficulty with urination, chest discomfort, problems with speech, cardiac irritability, and neurological disturbance have been noted only when patients receive more than 3mg/kg of bupivacaine. In this study, we are using less than 1mg/kg, which is a lot lower than the maximum amount of medication given to patients.

It is well known that bupivacaine can cause adverse effects (cardiotoxicity, and central nervous system toxicity); however, the dose and route of administration in our study minimizes these risks, as noted above.

Thrombin: Major risks of thrombin have only been seen in systemic usage. We are using thrombin only topically, in order to minimize side effects that may occur when used systemically. Topical thrombin per

CONFIDENTIAL

the FDA has risks of anaphylactic reactions that may occur in the clinical trial with similar frequency in the two study groups. The most common adverse event reported was procedural complications and pruritus. This risk is seen in patients with amide anesthetic sensitivity and we will screen patients for this preoperative and exclude patients with this potential risk.

Tranexamic acid: Major risks of tranexamic acid have only been seen in systemic usage. We are using tranexamic acid only topically, in order to minimize side effects that may occur when used systemically. For topical tranexamic acid according to the FDA, the most common adverse reactions are nausea, vomiting, diarrhea, allergic dermatitis, giddiness, hypotension, and thromboembolic events.

Aminocaproic acid: Major risks of aminocaproic acid have only been seen in systemic usage. We are using aminocaproic acid only topically, in order to minimize side effects that may occur when used systemically. For topical aminocaproic acid according to the FDA, it is generally well tolerated. The following adverse experiences have been reported: General: Edema, headache, malaise. Hypersensitivity Reactions: Allergic and anaphylactoid reactions, anaphylaxis. Cardiovascular: Bradycardia, hypotension, peripheral ischemia, thrombosis. Gastrointestinal: Abdominal pain, diarrhea, nausea, vomiting. Hematologic: Agranulocytosis, coagulation disorder, leukopenia, thrombocytopenia. Musculoskeletal: CPK increased, muscle weakness, myalgia, myopathy (see WARNINGS), myositis, rhabdomyolysis. Neurologic: Confusion, convulsions, delirium, dizziness, hallucinations, intracranial hypertension, stroke, syncope. Respiratory: Dyspnea, nasal congestion, pulmonary embolism. Skin: Pruritis, rash. Special Senses: Tinnitus, vision decreased, watery eyes. Urogenital: BUN increased, renal failure. There have been some reports of dry ejaculation during the period of AMICAR treatment. These have been reported to date only in hemophilia patients who received the drug after undergoing dental surgical procedures. However, this symptom resolved in all patients within 24 to 48 hours of completion of therapy.

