5.1 Inclusion Criteria

In order to be eligible to participate in this study, an individual must meet all of the following criteria:

1. Age 18 or older
2. Any patient undergoing elective hand surgery

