7.2 Study Schedule

Screening/Baseline Visit (up to 3 months prior to day of surgery)

- Obtain informed consent of potential participant verified by signature on written informed consent for screening form.
- Review medical history to determine eligibility based on inclusion/exclusion criteria.
- Review medications history to determine eligibility based on inclusion/exclusion criteria.
- Perform medical examinations needed to determine eligibility based on inclusion/exclusion criteria.
- Schedule day of surgery where primary intervention will be performed.
- Provide participants with information regarding tranexamic acid, and operative steps for administration of drugs into surgical wound prior to closure.
- Provide participants with log books.
- Randomize patient using sealed envelope method.

Day of Surgery

- Verify patient still meets inclusion/exclusion criteria.
- Administer study treatment
- Patient fills out Day 1 of pain diary

Intermediate Visits

- Participants will be called via phone each day by the study team to ensure they have completed their daily log of numerical pain rating scale and number of pain pills taken.
- They will arrive for an intermediate visit on their first postoperative visit (variable time, between 3-14 days postoperatively). Log books will be collected only after postoperative day 14.

Final Study Visit (up to 6 weeks post surgery)

CONFIDENTIAL

This material is the property of the NYU School of Medicine and Langone Medical Center. Do not disclose or use except as authorized in writing by the study sponsor
Interventional Template Version: 11 January 2019

Pain logs will be collected from participants who have not already returned them to study staff. The participants will be released of their duties to the study once the log books have been returned to the physicians. They will continue their routine follow up per the follow up schedule for each hand surgery procedure. No additional data is collected for study purposes at post-op visits beyond data collected per standard of care.

8 Assessment of Safety

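### Section 2.4.1 lists clotting events for both antifibrinolytics, but no eligibility criterion or listed history item covers clotting history or drugs that affect clotting

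*Combined protocol and SAP*

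**What the plan says.** Section 2.2.1 hypothesises that adding an antifibrinolytic to thrombin and local anesthetic improves pain relief "through the formation of a stable clot that prolongs the effect of local anesthesia".

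Section 2.4.1 begins its tranexamic acid paragraph with a mitigation: "Major risks of tranexamic acid have only been seen in systemic usage". It says the same of aminocaproic acid and gives topical use as the way to limit side effects. The tranexamic acid paragraph then states, for the topical form, that "the most common adverse reactions are nausea, vomiting, diarrhea, allergic dermatitis, giddiness, hypotension, and thromboembolic events". The aminocaproic acid paragraph calls the topical form generally well tolerated and then lists reported events, without saying by which route they arose. They include "Cardiovascular: Bradycardia, hypotension, peripheral ischemia, thrombosis" and "Respiratory: Dyspnea, nasal congestion, pulmonary embolism", with stroke and coagulation disorder further on.

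Section 5.1 admits adults aged 18 or older and "Any patient undergoing elective hand surgery". The seven exclusions in 5.2 are traumatic open wound, chronic pain, narcotic addiction, recreational drug dependency, psychiatric pathology, allergy to local anesthetics, thrombin or tranexamic acid, and supra/infraclavicular block. The past history named in 7.1.1 follows much the same list. Section 7.2 asks staff to "Review medications history to determine eligibility based on inclusion/exclusion criteria".

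**The concern.** The risk section and the eligibility section do not meet. The protocol names clotting events as a risk of the two investigational additions, and its hypothesis depends on making a clot more stable. Nothing written would identify a patient with a previous clot or stroke, a clotting disorder or a drug that affects clotting, and nothing would prompt a decision about that patient.

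Exposure is a single application before wound closure, so it cannot be stopped once a problem appears. Eligibility is therefore the main control, and here it is silent on a risk that the protocol itself names.

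**Working it through.** The plan states no figure on this point to reproduce. The check sets the sections side by side and adds two calculations for scale.

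**1. Named risk against written control**

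| Risk in 2.4.1 | Criterion in 5.1 or 5.2 | Listed history item in 7.1.1 |
|---|---|---|
| Reactions tied to amide anesthetic sensitivity (thrombin paragraph) | Exclusion 6, allergy | Drug allergy |
| Thromboembolic events (topical tranexamic acid) | None | None |
| Thrombosis, pulmonary embolism, stroke, coagulation disorder (aminocaproic acid) | None | None |

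The criteria number 2 + 7 = 9, and 0 of the 9 address clotting. For the first row, 2.4.1 says outright that patients will be screened before surgery and excluded. The protocol therefore does turn a named risk into a criterion in one place, but not for clotting.

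**2. The medication review.** The reviews in 7.2 are made against the written criteria, and the day-of-surgery check re-verifies the same criteria. A medication history can still exclude someone, because it may reveal chronic pain, addiction, psychiatric illness or allergy (exclusions 2 to 6). It cannot exclude anyone for taking an anticoagulant or antiplatelet drug, because no criterion refers to one.

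**3. The IND-exemption statement.** Item (iii) in 2.2 says that route, dosage, population and other factors do not significantly increase risk, and it cites 2.2.2. Section 2.2.2 gives doses and literature on topical use. It does not discuss which patients may be enrolled, so the population part of the statement has no support at the place cited.

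**4. Later safeguards**
- The halting rule (8.5) and 48-hour IRB reporting (8.4.1, 8.4.2) apply to unexpected related events. Under 8.2.3 an event is unexpected if its nature, severity or frequency does not fit the risk information already given. A thromboembolic event is already described in 2.4.1, so it may count toward neither.
- The PI reviews all data annually (8.6), while recruitment is expected to take 2 to 3 months (5.4).
- Section 5.7.1 allows participation to be ended for a medical condition. It does not restrict entry.

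**5. Could the trial show that the topical route is safe enough?** Planned antifibrinolytic patients: 2 arms × 10 = 20. With zero events in n patients, the one-sided 95% upper bound on the event rate is 1 − 0.05^(1/n).
- n = 20: 1 − 0.05^(1/20) = 13.9%
- n = 10 (one arm): 1 − 0.05^(1/10) = 25.9%

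An event-free trial would still be compatible with a rate of nearly 14%, so the trial's own data cannot replace a decision at entry.

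**6. Chance that the gap is met in practice.** The documents give no prevalence. If a share p of patients had a relevant history or medication, the chance of at least one among 40 is 1 − (1 − p)^40:
- p = 5%: 87%
- p = 10%: 98.5%
- p = 20%: 99.99%

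These p values are assumptions. They pool patients with past clots and patients on blood-thinning drugs, whose risks point in opposite directions. The result says only that meeting such a patient is plausible. It does not give the event risk.

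**The case against.** The strongest reply is that the sponsor did not overlook the risk but answered it with the route of administration. Section 2.4.1 attributes the major risks of both drugs to systemic use. Section 2.2.2 calls topical tranexamic acid safe and effective for reducing blood loss, and it cites topical trials using 1 to 2.5 g of tranexamic acid and 24 g of aminocaproic acid, against 500 mg and 1000 mg here. This stands as a stated mitigation and may prove sufficient. It does not close the gap. Section 2.4.1 still lists thromboembolic events for the topical form. The trials whose doses are listed are described as drug in saline, with no mention of thrombin. Nowhere is it argued that route makes a clotting criterion unnecessary.

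It is also fair to say that the 7.1.1 history is introduced as including its items, so a surgeon may ask more. In addition, 5.7.1 could act between randomisation and surgery. Both are true, but neither gives a rule for acting on the answer. Removal after randomisation would also cost one patient from an arm planned at 10.

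A reader might infer that patients with impaired clotting dilute the effect in arms 2 to 4. The documents neither state nor quantify this, and 2.2.1 says topical thrombin directly activates the last stages of clot formation at the site. Blunting by every anticoagulant or antiplatelet drug therefore cannot be assumed. For scale only, 10 per arm gives 80% power for (1.960 + 0.842) × √(2/10) = 1.25 SD (two arms, two-sided 0.05, normal approximation). If 5% or 10% of patients had no added effect at all, power would fall to about 76% or 71%. That is an illustration and not part of the finding.

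**Conclusion.** The concern holds as a gap between the risk section and the eligibility section. Clotting events are named for both antifibrinolytics. No criterion and no listed history item covers clotting history or clotting drugs, and the population part of the IND-exemption statement is unsupported where it points. Followed as written, the plan allows such patients into arms planned to hold 20 of the 40 participants, and the later safeguards act mainly on unexpected events.

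The number of patients affected and their excess risk cannot be derived from the documents. Two stronger readings are not supported. One is that the sponsor ignored the risk, when it relied on the topical route. The other is that efficacy is diluted, which no section establishes. The documents also do not show which patients should be excluded. That is a clinical judgement for the investigator.

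**What to change.** Before enrolment, reconcile 2.4.1 with 5.2.

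- Add clotting history and current anticoagulant or antiplatelet use to the history items in 7.1.1, so that the 7.2 reviews capture them.
- Have the investigator do one of two things: add a matching eligibility criterion in 5.2, with its clinical content and look-back window set by the investigator, or state in 2.4.1 and 2.2.2 why the topical route makes one unnecessary.
- Either way, give the population part of the IND-exemption statement a basis in 2.2.2.

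The cost is one more history item and a short text change, with no new test or visit. If a criterion is added, slightly fewer patients may be eligible and the population would be somewhat narrower.

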2.4.2 Known Potential Benefits

If this study shows improved pain control in the immediate postoperative period, decreased opioid use by patients will be a major benefit. If this study has a proven impact on postoperative pain control without the utilization of opioid pain medication, then the number of prescription medications will be reduced thus reducing cost of filled opioid prescriptions. However, we cannot guarantee subjects will benefit directly from being in the study. It is hoped that the knowledge gained from this study will help others in the future.

3 Objectives and Purpose

3.1 Primary Objective

The primary objective of this study is to evaluate the effectiveness of topical antifibrinolytics, thrombin and local anesthetics on postoperative pain control in patients undergoing elective hand surgery. We want to determine the efficacy of this treatment over treatment with thrombin and local anesthetics and just local anesthetics alone to the same population of patients.

3.2 Secondary Objectives (if applicable)

The secondary objective of the study is to reduce the amount of opioid pain medications required postoperatively for routine hand surgery procedures.

4 Study Design and Endpoints

4.1 Description of Study Design

The study is a single blinded placebo-controlled prospective randomized controlled trial. Patients will be randomized into one of four groups:

1. Topical lidocaine and bupivacaine alone
2. Topical lidocaine and bupivacaine with thrombin
3. Topical lidocaine and bupivacaine with thrombin and tranexamic acid

CONFIDENTIAL

This material is the property of the NYU School of Medicine and Langone Medical Center. Do not disclose or use except as authorized in writing by the study sponsor
Interventional Template Version: 11 January 2019

4. Topical lidocaine and bupivacaine with thrombin and aminocaproic acid

Patients meeting inclusion criteria will be randomized at their preoperative appointments and an initial evaluation will be completed for pre-operative pain levels using the numerical pain rating scale. At the conclusion of their respective surgery just prior to wound closure, the appropriate medications will be topically administered into the wound and the wound will be closed via standard method. Patients will record pain scores at home daily and also record the amount of pain pills needed postoperatively until post operative day 14. Analysis will be completed to ascertain the difference between preoperative and postoperative scales after 14 days among the four groups. We will also analyze the differences in the amount of opioid pain pills needed postoperatively among the four study groups.

4.2 Study Endpoints

4.2.1 Primary Study Endpoints

Comparison of pain levels using a visual analog scale preoperatively and postoperatively

4.2.2 Secondary Study Endpoints

Number of pain pills used

Total time in PACU

5 Study Enrollment and Withdrawal

5.1 Inclusion Criteria

In order to be eligible to participate in this study, an individual must meet all of the following criteria:

1. Age 18 or older
2. Any patient undergoing elective hand surgery

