Brief Summary	
This study is a prospective randomized trial examining the effect of tranexamic acid (TXA) and aminocaproic acid (ϵ-Ahx) with local anesthetics and thrombin in all electively created surgical wound beds in hand surgery to provide long term pain relief and decrease the use of postoperative narcotics.
 
All surgical created wounds for any hand surgery will be treated in a randomized fashion with the following four arms:
 
1. Bupivacaine + lidocaine2. Bupivacaine + lidocaine + thrombin3. Bupivacaine + lidocaine + thrombin + tranexamic acid4. Bupivacaine + lidocaine + thrombin + aminocaproic acid 
All are applied topically to surgical bed prior to closure of skin.

Phase	N/A
Objectives	
The primary objective of this study is to evaluate the effectiveness of topical antifibrinolytics, thrombin and local anesthetics on postoperative pain control in patients undergoing elective hand surgery. We want to determine the efficacy of this treatment over treatment with thrombin and local anesthetics and just local anesthetics alone to the same population of patients.
 
The secondary objective of the study is to reduce the amount of opioid pain medications required postoperatively for routine hand surgery procedures.

Methodology	Prospective single blinded study
Endpoint	Degree of pain and amount of adjuvant pain medication used at 1 month post surgery
Study Duration	12 months
Participant Duration	Pre-operative visit occurs up to 3 months prior to surgery Final Study visit occurs up to 6 weeks after surgery. Primary endpoint (returning completed pain diary to study staff) occurs at Day 14. Participants remain enrolled in the study up until their standard of care post-op visit, which typically occurs 4-6 weeks after surgery. Participation is complete when participants complete their final standard of care post-op visit.
Duration of IP administration	Applied topically to surgical bed prior to closure of skin
Population	Nontraumatic, elective upper extremity (hand) surgery cases, age 18 or older
Study Sites	NYU Langone Health Bellevue Hospital Center
Number of participants	40 (10 per study arm)
Description of Study Agent/Procedure	Applied topically to surgical bed prior to closure of skin: 1. Bupivacaine + lidocaine (reference therapy) 2. Bupivacaine + lidocaine + thrombin 3. Bupivacaine + lidocaine + thrombin + tranexamic acid 4. Bupivacaine + lidocaine + thrombin + aminocaproic acid

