10.1 Statistical and Analytical Plans (SAP)

10.1.1 General Approach

Each arm of this randomized, single-blinded, placebo-controlled study will have a minimum of 10 patients. There will be a minimum of 40 patients in the study. Patients will be randomized using Microsoft Excel.

Simple randomization will be used to determine the treatment arm. In order for us to power our study based on a previous similar study at NYU for topical application (Haddock et al., Thrombin and Topical Local Anesthetic for Postoperative Pain Management), we will need 10 patients for each individual treatment arm to detect any difference in the outcome.

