10.1.2 Analysis of the Primary Efficacy Endpoint(s)

Data will be expressed either as a mean (SD) or median and interquartile range (IQR). To evaluate PACU time as a function of each group, a one way analysis of variance test followed by a Tukey-Kramer post hoc test will be performed. To assess the number of pain pills need as a function of each group, a Kruskal-Wallis test followed by a Dunn post hoc analysis will be performed. To compare pain levels between the treatment arms, pain scores on a scale of 1 (lowest aka no pain) to 10 (highest pain experienced in life) will be collected daily via a patient log. They will be analyzed as a change from baseline (preoperative) pain levels and analyzed used a series of two proportion z tests with a family error rate equal to 0.05. For all tests, a P value of less than 0.05 will be considered statistically significant.

Pain is a subjective measure. We will be using an analog pain scale and reference them to the patients pre and postoperatively to account for this. Patients may take over the counter pain medication postoperatively. We cannot control the patient's use of over the counter pain medications while at home, thus we will have to rely on their accuracy and honesty for this study.

Patients will be called daily to ensure completion of daily log books. If they are not able to do this, they will be removed from the study analysis. If the patients return to clinic at 4-6 weeks post-surgery and they have completed their logs, their data will still be accepted. But if there is missing data, they will be removed from the analysis.

11 Source Documents and Access to Source Data/Documents

All data will be stored on HIPAA compliant and encrypted REDCap, approved by the institution and managed by MCIT.

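### Procedure type is known before randomisation but is used in neither the allocation nor any analysis: an optional gain in precision, not an error in the plan

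*Combined protocol and SAP*

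**What the plan says.** Eligibility in Section 5.1 is age 18 or older plus "Any patient undergoing elective hand surgery". The Protocol Summary is equally broad: "All surgical created wounds for any hand surgery will be treated in a randomized fashion with the following four arms". None of the seven exclusions in Section 5.2 restricts the kind of operation. Section 7.2 anticipates a mixture, since after the study "They will continue their routine follow up per the follow up schedule for each hand surgery procedure".

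On allocation, Section 10.1.1 states: "Simple randomization will be used to determine the treatment arm". Delivery is by sealed envelope (Sections 7.1.1 and 7.2), and no strata, blocks or minimisation are mentioned. Section 7.2 lists both the scheduling of surgery and randomisation under the screening visit, so the planned operation is known when the arm is assigned.

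On analysis, Section 10.1.2 compares arms only:
- PACU time: "a one way analysis of variance test followed by a Tukey-Kramer post hoc test will be performed".
- Pill count: Kruskal-Wallis, then Dunn.
- Pain: change from the preoperative score, tested by a series of two-proportion z tests.

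Procedure type is not a covariate, stratum or subgroup in any of these.

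**The concern.** Elective hand operations may differ in how much they hurt afterwards, and such a difference could carry through to pill count and PACU time. If so, procedure is a legitimate baseline covariate that costs almost nothing to collect. The only adjustment planned, change from preoperative pain, allows for pain before surgery and not for how painful the operation is. It also does not apply to pills or PACU time.

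Two things are at stake. Outcome variance that procedure could explain stays in the error term of a very small trial. And if one arm happens to receive more of the painful operations, nothing in the analysis corrects for it.

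**Working it through.** **The plan's own figure.** Section 10.1.1 says "we will need 10 patients for each individual treatment arm to detect any difference in the outcome", citing an earlier study. No effect size, SD, power or sidedness is given, so the 10 per arm cannot be reproduced. Working backwards, at 80% power and two-sided 0.05 for one pair of arms, the detectable difference is √(2/10) × (1.96 + 0.84) = 1.25 SD (1.32 SD for an exact t test), before any allowance for multiple comparisons.

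**Inputs.** From the documents: four arms, 10 per arm, significance level 0.05. Assumed, because the documents are silent: a share p = 0.4 of operations in a more painful class, a gap D of 1 or 2 points between classes, and a within-class SD s of 2 or 2.5 points. The working uses mean scores, not the proportions in the planned z tests.

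**1. How often arms differ in mix.** With Binomial(10, 0.4) painful operations per arm:
- a given pair of arms differs by 3 or more with probability 0.253;
- the most and least loaded of the four arms differ by 3 or more with probability 0.658 (0.60 if p = 0.3; 0.67 if p = 0.5).

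**2. What such an imbalance does.** A 3-patient imbalance with D = 2 shifts the difference in means by (3/10) × 2 = 0.6 points. The total SD is √(p(1−p)D² + s²):
- s = 2: √(0.96 + 4) = 2.23; SE of the difference = 2.23 × √(2/10) = 1.00; shift = 0.60 SE.
- s = 2.5: √(0.96 + 6.25) = 2.69; SE = 1.20; shift = 0.50 SE.

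At 1.32 SD the detectable difference is about 2.9 to 3.5 points, so the shift is roughly a fifth of it.

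**3. Type I error.** In simulation of two arms of 10 with p = 0.4 and D = 2, the unadjusted t test rejects a true null in 5.0% of trials overall. Given an imbalance of 3 or more, it rejects in about 8% to 9%. For D = 1 the conditional figure is about 6%.

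**4. What adjustment buys.** The share of variance explained is R² = p(1−p)D² / (p(1−p)D² + s²). The gain in effective sample size is [1/(1−R²)] / [1 + 1/(ν−2)], times the squared ratio of the t critical values on ν and ν−1 df. Here ν is the error df without the covariate: 36 for four arms of 10, and 18 for a single pair.

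| D | s | R² | 1/(1−R²) | Gain, four arms | Gain, one pair |
|---|---|---|---|---|---|
| 1 | 2 | 0.057 | 1.060 | 1.03 | 0.99 |
| 1 | 2.5 | 0.037 | 1.038 | 1.01 | 0.97 |
| 2 | 2 | 0.194 | 1.240 | 1.20 | 1.16 |
| 2 | 2.5 | 0.133 | 1.154 | 1.12 | 1.08 |

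**5. Larger gaps, and no gap.** These figures assume a 50:50 mix, s = 2, a true effect of 2.5 points and one pair of arms. Simulated power without and with the covariate is 66% and about 72% for a 2-point gap, 55% and about 72% for 3 points, and 46% and about 72% for 4 points. With no gap, adjusting lowers power from 75% to 72%.

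**The case against.** A reader might infer that chance differences in operation mix could overwhelm arms of 10, or that the planned comparisons are biased. The documents and the arithmetic do not support either reading. Variation due to procedure is already in the error term, and type I error stays at its nominal level over repeated randomisations. A 3-patient imbalance is common, but that would be true of any baseline factor of similar prevalence in a trial this size. Under the 2-point assumption it moves a contrast by only about half a standard error. Conditional type I error rates of 18% to 24% do arise, but only with gaps of 3 to 4 points together with an imbalance of 4 or more.

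Every input on size is assumed. Nothing in the protocol shows that procedure predicts the outcomes. The population is also described more narrowly elsewhere: outpatient procedures in Section 2.1 and routine ones in Section 3.2. Section 5.2 excludes supraclavicular and infraclavicular blocks, and Section 2.2.2 gives every arm a local block by the surgeon. These statements do not name operations, but they make a wide pain gap less certain.

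A practical objection is that two-proportion z tests cannot take a covariate, so using procedure for pain means changing that analysis. The choice of class is also a judgement: nothing in the documents favours one split over another.

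All of this stands. It limits the point to precision and to correcting the particular imbalance that occurs. It does not remove it, because the information is available before randomisation and costs almost nothing to use.

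**Conclusion.** The facts hold: eligibility is open to any elective hand operation, allocation is simple, and no analysis includes a procedure term. The consequence is modest and conditional. With 40% of operations in the more painful class and a within-class SD of 2 to 2.5 points, the covariate is worth about 1% to 3% more patients for a 1-point gap across four arms and about nothing for one pair. For a 2-point gap it is worth 12% to 20% across four arms and 8% to 16% for one pair. Larger gaps would make it worth more, but the documents give no basis for assuming them. This is an optional improvement. Adjustment would not cure the small sample: 10 per arm still detects only differences of about 1.25 SD or more.

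**What to change.** - Before randomisation, record one two-level procedure class defined in advance, for example bone or joint work versus soft tissue only.
- PACU time: add the class to the planned ANOVA, and apply the Tukey-Kramer comparisons to the adjusted arm means.
- Pain: replace the two-proportion z tests with a linear model for the pain score containing arm, baseline pain and class, keeping the family error rate at 0.05.
- Pill count: use a rank test stratified by class (van Elteren type), with multiplicity-controlled pairwise comparisons in place of Dunn.
- If the allocation list is regenerated in blocks, stratify by this class only; more strata would be too sparse with 40 patients.

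The cost is SAP wording, one CRF field, 1 degree of freedom and a class definition fixed before the first patient is randomised. If the class turns out not to predict outcome, a little power is lost: about 3 percentage points (75% to 72%) for one pair of arms under the assumptions above.
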